6.1 Data Collected

6.1.1 *Prior to the start of the experiment:*

- Age
- Sex
- Race and ethnicity

- Basic demographic information
- Date of last menstrual period in pre-menopausal participants
- Approximate date of diabetes diagnosis
- Medical, surgical, and social history, allergies and review of systems relevant to inclusion and exclusion criteria
- Medications (prescription and non-prescription) and date of last change in medication regimen
- Duration of insulin pump and CGM use, if applicable
- Type of insulin(s) currently used
- Insulin regimen (basal rate, sensitivity factor, and carbohydrate ratio for pump and if known for MDI; otherwise doses and schedule for MDI, sliding scale/correction if applicable)
- Average total daily dose of insulin in the last 30 days from pump data and/or self-reported estimate from MDI patient report
- Usage of CGM (type of CGM, days per month worn, usage of data, whether insulin dosing is based on CGM alone, alarm settings), if applicable
- Height and weight (height will be self-reported for TH participants)
- Urine HCG (pre-menopausal participants)
- Hemoglobin A1c

6.1.2 *During study arms*

- CGMG (CGM glucose) every five minutes from the Dexcom CGM
- All fingerstick BG measurements taken by the participant (meter download)
- Average glucose target used
- Insulin total daily dose from bionic pancreas download
- Timing of meal announcements and size of meals announced from bionic pancreas download
- Time participants were not under bionic pancreas control
- Information collected from the daily survey:
 - Number of reported hypoglycemic events requiring carbohydrate intervention
 - Total grams of carbohydrates taken to prevent or treat hypoglycemia
 - Number of severe hypoglycemic events (defined as participant required assistance to treat)
 - Number of unscheduled insulin cartridge/infusion set changes
 - Time disconnected from the iLet (for participants on the BP arm)
- Data from questionnaires about quality of life, attitudes and expectations regarding the bionic pancreas at baseline and on day 14 of each arm.
- Number of and reasons for unscheduled visits and phone calls
- Device malfunctions requiring study team contact and other reported device issues
- Type of automation used, if any, by participants in the EN group

6.2 Primary endpoint

- Percentage of individuals with mean CGM glucose <183 mg/dL (corresponding to an estimated HbA1c of <8.0%) on days 3-14, by group.

6.3 Secondary endpoints

- Mean CGM glucose on days 3-14

- Percentage of time with CGM glucose <54 mg/dl on days 3-14
- Percentage of time with CGM glucose in the 70-180 mg/dl range on days 3-14
- Percentage of individuals with mean CGM glucose <154 mg/dL (corresponding to an estimated HbA1c of <7.0%) on days 3-14, by group.

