2.1 Primary objective

To assess the feasibility of deploying the iLet bionic pancreas system in the insulin-only configuration to

pump-naïve MDI users with type 1 diabetes, in the setting of being recruited from community-based primary care practices and being trained and managed by primary care providers (PC group), and in pump- and CGM-experienced (sensor-augmented pump or hybrid closed-loop) users with type 1 diabetes recruited from, trained, and managed by an academic endocrinology practice (EN group). In both practice settings, the exclusive use of telehealth (TH) visits will be assessed, as will use of in-person (IP) visits.

We will enroll 40 adult volunteers (18-85 years old) with type 1 diabetes, 20 who are insulin pump naïve MDI users enrolled from community primary care practices by University of Colorado Family Medicine (PC group) and 20 who are technology-savvy sensor-augmented pump or hybrid closed-loop users enrolled by the Massachusetts General Hospital Diabetes Clinical Research Center (EN group). Ten of the participants at each center will be trained and managed throughout the trial using in-person visits (PC-IP and EN-IP groups) and the other ten from each center will be trained and managed throughout the trial exclusively via telehealth visits (PC-TH and EN-TH groups). The 40 participants will be evenly divided into these four groups, but not by randomization. Participants will be assigned to either the in-person or telehealth arm based on the participant's preference, the participant's location, and the discretion of the investigator. Subjects in all four groups will each participate, in random order, in one 14-day study arm under their own usual care (UC arm) and one 14-day study arm under the insulin-only configuration of the iLet bionic pancreas (iLet arm).

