5.6 Study Visit Procedures

5.6.1 Visit Procedures for in-person (IP) visits

5.6.1.1 Day 1 Visit (Visit 2):

- The body weight of the participant will be documented.
- A urine pregnancy test will be performed in participants of child-bearing potential at the start of the first arm. If the test is positive, the participant will be informed of the result and the visit will be ended. The date of the last menstrual period will also be documented.
- Study staff will review any changes in the participant's medical history or medications to ensure continued eligibility, and any adverse events that may have occurred since their screening visit.

5.6.1.1.1 Participants randomized to usual care:

- Study staff will provide supplies and review the study procedures.
- Participants will be trained how to insert, maintain and use the Dexcom G6 (in blinded mode if they are not a CGM user).
- The participants will wear a Dexcom G6 sensor and study staff will confirm they are doing it properly.

5.6.1.1.2 Participants randomized to bionic pancreas:

- Study staff will provide supplies and review the study procedures.
- Participants will be trained how to insert, maintain and use the Dexcom G6 CGM.
- The participants will wear a Dexcom G6 sensor and study staff will confirm they are doing it

properly.

- Participants will be trained to use the iLet, including navigating the GUI, filling and installing cartridges and inserting infusion sets.
- Participants will set up the iLet and insert the infusion set and study staff will confirm they are doing it properly.
- The control algorithm will be initialized with the participant's weight.
- If using an insulin pump (EN group), their own insulin infusion pump will be stopped and disconnected if applicable, and its infusion set will be removed
- If using MDI therapy (PC group), they will be instructed not to take any additional insulin injections once the bionic pancreas is started, unless instructed to do so by study staff
 - Participants on multiple daily injections (MDI) may be started on the iLet without a need for adjustment of their long-acting insulin dose. The new equilibrium will not be reached until all the long-acting insulin has completely cleared their system, which may take 48 hours or more. Participants must be advised that they may see escalating dosing by the iLet during this period.

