 - Investigators may consider starting MDI users at the "higher" glucose target setting. If the "higher" setting is used, wait ~2 days before moving down to the default target.
- Participants will complete Clarke's Instrument for Impaired Awareness of Hypoglycemia.
 - Participants with a score > 4 will be instructed to check BG at 2am for the first 2 nights using the iLet

5.6.1.2 Mid-period Follow Ups (Visits 3, 4, 6, and 7):

- Study staff may supervise the first site change via a video visit, as needed or requested based on participant's prior experience and comfort level
- All participants will have a virtual phone visit on Day 2 and Day 5 (+/-2 days) to assess device adaptation, glucose control, and to answer any questions the participant may have
- Study staff will query the participant for any adverse events and assess the participant's ability to follow protocol and, if applicable, use the device at this time.

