6.4 Safety endpoints

- Frequency of adverse events
- Frequency of severe hypoglycemia
- Frequency of diabetic ketoacidosis, as defined within this protocol in Section 9.2.

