6.5 Other endpoints

- The percentage of time that valid CGM glucose readings are captured by the iLet
- The percentage of the time that the insulin pump channel of the iLet is available
- Percentage of time across days 3-14 within each of the following CGM glucose ranges:
 - < 70 mg/dl
 - > 180 mg/dl
 - > 250 mg/dl
- Percentage of time participants were disconnected from the iLet
- Number of episodes of symptomatic hypoglycemia (reported daily by participants)
- Percentage of participants with mean Dexcom CGMG <154 mg/dl (estimated average glucose corresponding to an A1c of <7.0%) on days 3-14
- Mean total daily dose of insulin in the iLet arms and in the usual care arms of the EN groups (from pump download) on days 3-14
- Mean daily basal insulin dose in the iLet arms and in the EN groups' usual care arms (from pump download) on days 3-14
- Mean daily bolus insulin dose in the iLet arms and in the EN groups' usual care arms (from pump download) on days 3-14
- Mean number of daily meal announcements in the iLet arms and meal boluses in the EN groups' usual care arms (from pump download) on days 3-14
- Glucose variability measured with coefficient of variation (CV) and with mean of daily difference (MODD) on days 3-14
- Number of unscheduled insulin cartridge/infusion set changes in the iLet arms
- Mean glucose target in the iLet arms
- Scores from psychosocial questionnaires (including quality of life, fear of hypoglycemia, and diabetes distress). These surveys will be collected at baseline and after each arm. Post-BP measurements, including the bionic pancreas user opinion survey, will be given only after the BP arm.

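### Days 1–2 on the iLet are recorded by CGM but enter no CGM glucose-range endpoint, although the study asks whether pump-naive users can be started on the device

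*Combined protocol and SAP*

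**What the plan says.** Each participant spends "one 14-day study arm under the insulin-only configuration of the iLet" system (section 2.1). The CGM range endpoints are windowed as follows:

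- Section 6.3: "Percentage of time with CGM glucose <54 mg/dl on days 3-14" and "Percentage of time with CGM glucose in the 70-180 mg/dl range on days 3-14".
- Section 6.5: "Percentage of time across days 3-14 within each of the following CGM glucose ranges", the ranges being <70, >180 and >250 mg/dl.

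The Protocol Summary gives the same windows for these five. The safety endpoints in section 6.4 are adverse events, "Frequency of severe hypoglycemia" and DKA. None has a day window and none is a CGM measure.

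On starting the iLet in MDI users, section 5.6.1.1.2 says they "may be started on the iLet without a need for adjustment of their long-acting insulin dose". It continues: "The new equilibrium will not be reached until all the long-acting insulin has completely cleared their system, which may take 48 hours or more". The telehealth text in 5.6.2.1.2 repeats both statements.

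Section 6.1.2 lists five-minute CGM data among the data collected during the arms, with no day-3 start.

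**The concern.** A run-in exclusion makes sense when the aim is to describe control after the algorithm has adapted. Here, part of the aim is the start itself: the hypothesis in section 2.1 is that pump-naive primary care participants can be started successfully, in person and by telehealth. The protocol's own warning about residual long-acting insulin points at the first two days, and it concerns the PC group (20 of 40 participants), because the EN group comes from pump therapy.

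Two readings of the results are affected. First, time <54 mg/dl is a key outcome for the similarity hypotheses in section 2.2 (PC versus EN, telehealth versus in-person). Those comparisons would be made only after the days in which the starting regimens differ most. Second, section 6.7.4 says that performance comparable to earlier trials would support safe use in primary care and by telehealth. It admits participants with at least 24 hours of CGM data within days 3–14. That exploratory inference therefore uses no start-up CGM data, and a participant who withdraws during days 1–2 adds nothing to it from that arm.

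**Working it through.** The plan gives no figure to reproduce on this point; section 6.6 states that no power or sample size calculation was done. The check is of coverage, followed by simple arithmetic.

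**What covers days 1–2 of the iLet arm**

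| Source | Covers days 1–2? | What it captures |
|---|---|---|
| Time <54, 70–180 (6.3); <70, >180, >250 mg/dl (6.5) | No | CGM ranges, days 3–14 only |
| Adverse events (6.4, 6.7.1) | Yes, from first exposure | Hypoglycemia only if another person had to assist (9.3.1) |
| Severe hypoglycemia, DKA (6.4) | Yes | Severe events |
| Symptomatic episodes (6.5) | Yes | Self-reported |
| Daily survey (5.7, 6.1.2) | Yes | Reported lows needing carbohydrate, grams taken |
| Alarm at ≤55 mg/dl with meter check (5.7.3) | Yes | Fingerstick and treatment, if the participant responds |
| Raw CGM (6.1.2) | Yes | Everything, but no endpoint uses it for these days |

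The remaining gap is a low that is not recognised or not treated. It is in the CGM file and in no endpoint.

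**Size of the omitted window** (scheduled readings, full 24-hour days, so upper limits)

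- Readings per day: 24 × 60 / 5 = 288.
- Per participant, iLet arm: 288 × 14 = 4,032. Days 1–2: 288 × 2 = 576. Days 3–14: 3,456.
- Share omitted: 2/14 = 14.3%.
- Per group of 10: 20 participant-days, 480 hours, 5,760 readings. PC group of 20: 40 participant-days, 960 hours, 11,520 readings.

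**Illustration with assumed values.** The documents give no days 1–2 rate for this population, so every rate below is an assumption.

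Whole-arm % = (2 × days 1–2 % + 12 × days 3–14 %) / 14.

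| Days 3–14 (what the plan reports) | Days 1–2 | Whole arm |
|---|---|---|
| 0.5% | 1% | (2 + 6)/14 = 0.57% |
| 0.5% | 2% | (4 + 6)/14 = 0.71% |
| 0.5% | 5% | (10 + 6)/14 = 1.14% |
| 0.6% | 1% | (2 + 7.2)/14 = 0.66% |
| 0.6% | 5% | (10 + 7.2)/14 = 1.23% |

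In hours, 1%, 2% and 5% of the 48 hours in days 1–2 are 0.48, 0.96 and 2.4 hours. The planned endpoint gives the same answer in each case. If days 1–2 resemble days 3–14, the two figures coincide and nothing is lost. A whole-arm average also dilutes an early excess, which is why days 1–2 should be shown separately.

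**The case against.** The strongest reply is that the start-up days are already watched. CGM runs throughout, the iLet alarms at ≤55 mg/dl from the first night, participants are trained to check and treat, and there is a Day 2 call. The daily survey asks about lows in the previous 24 hours, and the safety endpoints and stopping rules apply from the start. All of this stands. A reader might infer that the first two days go unmeasured, or that the trial would call initiation safe with no initiation data; the documents support neither. The safety analysis is descriptive, section 6.7 says p-values are not for inference, and the safe-use statement in 6.7.4 is exploratory.

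A second reply is precedent. The iLet bridging study, which included 12 MDI users among 34, showed Days 3–7 (Appendix A, 12.1.8), and a common window helps historical comparison. That supports keeping days 3–14 for the existing endpoints. It does not fill the gap, because that study's reported results also omit the first two days. The only reason given in the documents for dropping early days belongs to an earlier five-day study, where most adaptation fell on Day 1 and only Day 1 was dropped (12.1.2). No reason is given for a day-3 start here.

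Two further inferences go too far. One is that the window removes the whole transition: clearance of 48 hours or more can run into day 3 and beyond. The other is that the night checks show the protocol expects overlap hypoglycemia in MDI users. The text is "Participants with a score > 4 will be instructed to check BG at 2am for the first 2 nights using the iLet", which depends on hypoglycemia awareness and not on MDI use. The clearance warning itself tells participants to expect escalating iLet dosing; it does not mention hypoglycemia.

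**Conclusion.** The point holds as a reporting gap. Days 1–2 of the iLet arm are recorded, but all five CGM range endpoints leave them out, and section 6.4 has no CGM measure to make up for it. Unrecognised or untreated biochemical hypoglycemia at start-up therefore reaches no endpoint in a study about starting the device.

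The omitted share is certain: 14.3% of iLet time. The effect on reported hypoglycemia is unknown. It is zero if days 1–2 look like the rest, and 0.07 to 0.64 percentage points on time <54 mg/dl under the assumed 0.5% baseline with 1% to 5% on days 1–2 (0.57 − 0.5 and 1.14 − 0.5). The residual long-acting insulin argument applies to the PC group only. The primary endpoint and the days 3–14 window for efficacy are not in question. This is a cheap improvement to the plan and does not invalidate it.

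**What to change.** Keep days 3–14 for the primary and all existing secondary endpoints. Add to section 6.4 a descriptive summary, from the CGM data already collected, of the percentage of time <54, <70 and >250 mg/dl on days 1–2 and on days 1–14 of the iLet arm, by group (PC-IP, PC-TH, EN-IP, EN-TH). Use the same day boundary as the days 3–14 endpoints and report the table beside the other safety results. One sentence giving the reason for the day-3 start would also help.

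The cost is one endpoint line and one table, with no new procedures and no change in sample size. With 10 people per group, the two-day figures will be imprecise and should be read as descriptive. Reported hypoglycemia may look slightly less favourable. A split of usual-care days 1–2 by sequence is not needed: with balanced sequences it would leave about 5 people per cell.

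Separately, the basal-insulin instructions at iLet start differ. The telehealth text (5.6.2.1.2 and 5.6.2.3) tells MDI users to take no basal insulin from the morning of the visit, and 5.6.2.1.2 also carries the no-adjustment statement. The in-person text (5.6.1.1.2 and 5.6.1.3) lacks that instruction. These passages must be reconciled, because a difference between the in-person and telehealth groups at start-up could otherwise reflect the instructions and not the mode of care.

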6.4 Safety endpoints

- Frequency of adverse events
- Frequency of severe hypoglycemia
- Frequency of diabetic ketoacidosis, as defined within this protocol in Section 9.2.

6.5 Other endpoints

- The percentage of time that valid CGM glucose readings are captured by the iLet
- The percentage of the time that the insulin pump channel of the iLet is available
- Percentage of time across days 3-14 within each of the following CGM glucose ranges:
 - < 70 mg/dl
 - > 180 mg/dl
 - > 250 mg/dl
- Percentage of time participants were disconnected from the iLet
- Number of episodes of symptomatic hypoglycemia (reported daily by participants)
- Percentage of participants with mean Dexcom CGMG <154 mg/dl (estimated average glucose corresponding to an A1c of <7.0%) on days 3-14
- Mean total daily dose of insulin in the iLet arms and in the usual care arms of the EN groups (from pump download) on days 3-14
- Mean daily basal insulin dose in the iLet arms and in the EN groups' usual care arms (from pump download) on days 3-14
- Mean daily bolus insulin dose in the iLet arms and in the EN groups' usual care arms (from pump download) on days 3-14
- Mean number of daily meal announcements in the iLet arms and meal boluses in the EN groups' usual care arms (from pump download) on days 3-14
- Glucose variability measured with coefficient of variation (CV) and with mean of daily difference (MODD) on days 3-14
- Number of unscheduled insulin cartridge/infusion set changes in the iLet arms
- Mean glucose target in the iLet arms
- Scores from psychosocial questionnaires (including quality of life, fear of hypoglycemia, and diabetes distress). These surveys will be collected at baseline and after each arm. Post-BP measurements, including the bionic pancreas user opinion survey, will be given only after the BP arm.

6.6 Sample Size Determination

No formal statistical power or sample size calculations have been done for this study. This study is primarily intended to be a feasibility trial to verify that the iLet can be managed by both primary care physicians, endocrinologists, and delivered through telehealth.

6.7 Statistical Analyses

An intention-to-treat analysis will be performed. Descriptive statistics will be used to summarize patient characteristics and assessments. We will estimate the percentage of participants who have a mean sensor glucose <183 mg/dl in the iLet arms of all four groups (PC-IP, PC-TH, EN-IP, EN-TH), along with confidence intervals using the Clopper-Pearson method. The hypothesis is that there is no difference in the percentage of each group that meet this metric.

The primary analysis of the designated endpoints will be calculated on an intention-to-treat basis. In cases where an arm was not completed, we will use the available data from that arm in the data analysis. We will calculate percentages, means, standard deviations (and medians and interquartile ranges as appropriate), and ranges in descriptive analyses. Unless otherwise specified, continuous data will be summarized by presenting the number of non-missing observations, mean and standard deviation (SD) or median, minimum, and maximum. Categorical data will be summarized by presenting the number of patients and percentage for each category. We will use the t-test for comparisons of means for normally distributed outcomes and the Mann-Whitney U test for comparisons of medians on non-normally distributed outcomes between groups (PC-IP, PC-TH, EN-IP, EN-TH). We will use the paired t-test for comparison of means for normally distributed outcomes and the Wilcoxon Signed Rank test for comparisons of medians on non-normally distributed outcomes when comparing between iLet and usual care within groups. There will be no adjustments for multiple comparisons.

We may, in exploratory analyses, also stratify subjects for secondary analyses of the pre-specified endpoints by the following characteristics: sex, age, usual care insulin total daily dose, body mass index, baseline A1c, and use of CGM in usual care.

P-values can be displayed to aid interpretation, not for inference. Tables, figures and listings of all primary, secondary and safety endpoints will be created.

Data from periods when the bionic pancreas was not in use will be included, if available (Dexcom CGM data may not be available in some failure modes).

All questionnaire data (including quality of life data) for patients who have completed a minimum of 4 days with a device will be included. Results will be compared by Wilcoxon signed-rank test.

6.7.1 *Safety Analyses*

No inferential tests of safety data will be performed. Descriptive summaries of safety data will be presented. Treatment-emergent AEs are defined as AEs with onset date on or after the first day of exposure to randomized treatment.

6.7.2 *Baseline Descriptive Statistics*

The number and percentage of patients who were screened, randomized, discontinued (with reason for discontinuation), and completed the trial will be summarized descriptively for all screened patients. Baseline and demographic data will be summarized using descriptive statistics. All comparisons will be between treatments within patients. Listings of de-identified individual patient data will be presented.

6.7.3 *Tabulation of Individual participant Data*

Listings of de-identified individual patient data will be presented.

6.7.4 *Exploratory Analyses*

The performance of the iLet in each period can be compared with historical data from previous bionic pancreas trials. If the performance of the iLet in this study is comparable to our previous data, that will support the hypothesis that the iLet can be safely used in primary care settings and via telehealth. All participants with at least 24 hours of CGM data during days 3-14 of any treatment periods will be included in these analyses.

7 Risks and Discomforts

Participants may experience mild discomfort associated with the insertion of infusion sets and the Dexcom CGM sensor into the SC tissues. The risk of discomfort due to insertion of infusion sets and sensors may be greater than in their lives outside the trial because more infusion sets and sensors are required than are used in usual care, and some participants will have only used MDI.

There is a risk of hypoglycemia. This risk is expected to be similar to or less than the risk during the participants' lives outside of the trial based on data from earlier trials. All of our previous studies have shown that hypoglycemia is reduced in all configurations of the bionic pancreas when compared with usual care.

There is a risk of hyperglycemia. This risk is expected to be less than the risk during the participants' lives outside of the trial based on data from earlier trials. All of our previous studies have shown that hyperglycemia is significantly reduced in all configurations of the bionic pancreas when compared with usual care.

8 Potential Benefits

It is expected that this protocol will yield increased knowledge about the safety and efficacy of the iLet bionic pancreas managed in care models previously untested (PCP in-person, PCP via telemedicine, and endocrinology via telemedicine). The individual participant may not benefit from study participation.

Based on evidence from previous trials of the bionic pancreas and the design of this trial, participants enrolled in the study may benefit from a reduction in risk of hypoglycemia and hyperglycemia and a closer to physiologic mean glucose than they typically achieve with their usual care.

Participants will be financially compensated for participating in the study.

9 Data and Safety Monitoring

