Our hypothesis is that pump naïve community-based primary care participants can be successfully started on the iLet bionic pancreas system by primary care providers in-person and via telehealth and that we will see similar glucose control by the iLet in the primary care and academic endocrinology groups and in the telehealth and in-person groups, with a target mean glucose of < 183 mg/dl in all four groups (PC-IP, PC-TH, EN-IP, and EN-TH). This target of < 183 mg/dl is a functional and clinically meaningful threshold for each group, consistent with a quality indicator of diabetes management (estimated HbA1c < 8.0%) that corresponds to the NCQA HEDIS measure of "HbA1c control" and which is therefore used frequently by many payers, reporting, and accrediting bodies. The outcome is categorical, and the primary outcome is not a direct comparison of the mean CGM glucose between the groups.

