2.2 Secondary objectives

1. To obtain preliminary data on the quality of glycemic control among the PC and EN groups, with separate analyses in the IP and TH sub-groups, and in the UC and iLet arms within those groups, which will be used to power a larger study with a glycemic control metric as the primary outcome. Our hypotheses are that glycemic control, with key outcomes being group mean CGM glucose, the group mean time with CGM glucose less than 54 mg/dl, and the group mean time with CGM glucose in the 70–180 mg/dl range, will be similar in the PC-IP group and the EN-IP group, and in the PC-TH group and the EN-TH group in the iLet arm. Additionally, we hypothesize that glycemic control will be similar in the PC-TH group and the PC-IP group, and in the EN-TH group and the EN-IP group in the iLet arm. Further, we hypothesize that there will be a larger difference in glycemic control metrics between the UC arms versus the iLet arm in the PC group than there will be in the EN group.
2. To assess the impact of the insulin-only configuration of the iLet bionic pancreas system on psychosocial outcomes (including quality of life, fear of hypoglycemia, and diabetes distress) among study participants. Secondary analyses will be conducted between the telehealth and in-

person arm, the EN and PC groups, and the iLet and UC arms.

3 Participant Selection

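### Section 6.7 hypothesises no difference between groups in the primary proportion, but plans only a separate interval for each group of 10 and nothing that estimates a difference

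*Combined protocol and SAP*

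**What the plan says.** Section 6.2 defines the primary endpoint as the percentage of individuals, by group, whose mean CGM glucose on days 3 to 14 is below 183 mg/dl. Section 6.7 says this percentage will be estimated "in the iLet arms of all four groups (PC-IP, PC-TH, EN-IP, EN-TH), along with confidence intervals using the Clopper-Pearson method". No confidence level is stated. The next sentence reads: "The hypothesis is that there is no difference in the percentage of each group that meet this metric".

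The between-group methods that follow are for other kinds of outcome: "We will use the t-test for comparisons of means for normally distributed outcomes and the Mann-Whitney U test for comparisons of medians". The section adds: "P-values can be displayed to aid interpretation, not for inference". Section 6.6 says that no power or sample size calculation was made and describes a feasibility trial.

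The comparison is part of the study's stated aims. The hypothesis in section 2.1 (repeated in the Protocol Summary) expects "similar glucose control by the iLet in the primary care and academic endocrinology groups and in the telehealth and in-person groups". Section 2.2 carries the idea into the secondary glycemic outcomes, which "will be similar in the PC-IP group and the EN-IP group, and in the PC-TH group and the EN-TH group in the iLet arm". It also expects that "glycemic control will be similar in the PC-TH group and the PC-IP group, and in the EN-TH group and the EN-IP group". Nowhere is similarity given a numerical meaning. Section 2.1 puts ten participants in each group, "evenly divided into these four groups, but not by randomization".

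**The concern.** A Clopper-Pearson interval describes one proportion. Four of them, one per group, do not estimate how far any two groups differ, and the t-test and Mann-Whitney test are not specified for a binary endpoint. The plan therefore states a between-group hypothesis on its primary endpoint and gives no analysis that addresses it.

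The risk lies in how the result will be read. Four percentages that look alike, with wide overlapping intervals, could be reported as showing no difference when large differences remain compatible with the data. High percentages in every group are plausible here. Table 2 (section 1.3.3) gives 155 ± 13 mg/dl for the insulin-only iLet with lispro or aspart in the adult bridging study. If participant means were roughly normal, about 98% would fall below 183, since (183 − 155)/13 = 2.15. That cohort may differ from this one. Still, results near the ceiling in all four groups would look like confirmation.

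**Working it through.** **Inputs.** There are ten participants per group, so 20 per side when primary care is set against endocrinology or telehealth against in-person (section 2.1). The endpoint is binary (section 6.2). The 95% level is an assumption, because none is stated, and the counts are illustrative. The plan gives no power, margin or difference, so there is no figure of its own to reproduce.

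**What the planned intervals show.** Clopper-Pearson 95% intervals at n = 10:

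- 10/10: 69.2% to 100%
- 9/10: 55.5% to 99.7%
- 8/10: 44.4% to 97.5%
- 7/10: 34.8% to 93.3%
- 4/10: 12.2% to 73.8%

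The intervals for 10/10 and 4/10 overlap although the observed gap is 60 points. A group at 10/10 separates only from one at 3/10 or lower. Overlap is therefore no guide to similarity.

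**The missing quantity.** Newcombe's interval combines the Wilson limits (l, u) of each proportion:

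lower = (p1 − p2) − √[(p1 − l1)² + (u2 − p2)²]

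upper = (p1 − p2) + √[(u1 − p1)² + (p2 − l2)²]

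When every participant succeeds, the Wilson limits are l = n/(n + 1.96²) and u = 1.

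- n = 10: l = 10/13.84 = 0.722. For 10/10 v 10/10 the half-width is √[(1 − 0.722)² + 0²], or 27.8 points.
- n = 20: l = 20/23.84 = 0.839. For 20/20 v 20/20 the half-width is 16.1 points.
- 9/10: Wilson limits 0.596 and 0.982. For 9/10 v 9/10 the half-width is √[(0.900 − 0.596)² + (0.982 − 0.900)²], or 31.5 points.

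Miettinen-Nurminen intervals give the same picture:

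| Observed | Difference (points) | Newcombe 95% | Miettinen-Nurminen 95% |
|---|---|---|---|
| 10/10 v 10/10 | 0 | ±27.8 | ±28.8 |
| 9/10 v 9/10 | 0 | ±31.5 | ±33.7 |
| 20/20 v 20/20 | 0 | ±16.1 | ±16.5 |
| 18/20 v 18/20 | 0 | ±21.4 | ±22.3 |
| 10/10 v 9/10 | +10 | −18.9 to 40.4 | −20.4 to 41.3 |
| 20/20 v 19/20 | +5 | −11.6 to 23.6 | −11.9 to 23.9 |

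Pooling narrows the interval but does not by itself establish the absence of a difference.

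**Why a test would not help.** Fisher's exact test at two-sided 0.05 with 10 v 10 has power of 5.7% for true rates of 90% v 70%, and 29.5% for 90% v 50%. A non-significant result would be expected even when the true difference is large.

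**The case against.** The strongest reply is that this is a declared feasibility study which never undertakes to declare equivalence. It has no success rule, no power calculation and no inferential use of p-values. Its primary endpoint is defined by group, and a percentage with an exact interval per group is the right analysis of that. Section 2.1 also says that the primary outcome is not a direct comparison of mean CGM glucose between groups. The secondary similarity hypotheses concern mean glucose and times in range, for which between-group tests are planned. A reader could work out any difference from the reported counts. On this view, rewording one sentence would be enough.

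Much of this stands. The per-group intervals should stay, no larger sample is called for, and the gap concerns the binary endpoint only. It is also why the remedy is estimation.

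The reply does not remove the point. The disclaimer in section 2.1 covers mean glucose, whereas section 6.7 goes on to state a between-group hypothesis on the proportions. Rewording that sentence alone would leave the similarity hypothesis in section 2.1 with no analysis of the primary endpoint behind it. Leaving readers to derive differences means that contrasts and pooling are chosen after the data are seen.

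The contrasts are also not randomised, so an interval could be over-read as an effect of the care model. That is a reason to report it with a caveat, not to leave the comparison to inspection.

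**Conclusion.** The concern holds. The plan states a hypothesis of no difference on its primary proportion and contains no analysis that could support it. With identical observed results, the largest difference not ruled out is about 28 to 32 points between groups of 10 and 16 to 21 points at 20 v 20 (Newcombe), for success rates of 90% to 100%. These figures assume a 95% level, full enrolment and illustrative counts. The Miettinen-Nurminen limits are slightly wider.

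This should be corrected, but it does not undermine the trial. The per-group analysis fits the endpoint as defined, and the fault is the mismatch between hypothesis and analysis. A lesser conflict of wording sits in section 6.7.2, where a sentence under baseline statistics describes every comparison as a within-patient one between treatments. Section 6.7 plans between-group comparisons.

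**What to change.** 1. Replace the hypothesis of no difference in section 6.7 with an aim to estimate the differences between groups, and align the similarity wording in section 2.1 with it.
2. Report the difference in the primary proportion, with a 95% Newcombe or Miettinen-Nurminen interval, for primary care v endocrinology and telehealth v in-person (20 v 20 each). Show alongside the four contrasts that section 2.2 names for glycemic control: PC-IP v EN-IP, PC-TH v EN-TH, PC-TH v PC-IP and EN-TH v EN-IP. Keep the per-group Clopper-Pearson intervals and state their level.
3. Report the largest difference not ruled out. Do not conclude that groups are similar or do not differ unless the interval excludes a difference that the sponsor has named beforehand. State with the result that the contrasts are not randomised: primary care v endocrinology coincides with site and with prior injection v pump use, and visit type follows preference, location and investigator discretion.
4. Reconcile the within-patient sentence in section 6.7.2 with the between-group comparisons in section 6.7.

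The cost is SAP wording and a small table from data already collected, with no extra participants or visits. The price is a more modest conclusion.
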